
Gains in metacognitive regulation capacities predict clinical improvement. In the 2018 RCT,²⁶ we tested a mediational model and found that measures of self-reported overall and specific attentional and metacognitive regulatory ability demonstrated indirect effects on diagnostic anxiety

severity, worry, depression, functionality, and QOL when comparing ERT to a modified attention control (MAC) condition. Further, self-reported metacognitive skills (i.e., reappraisal and decentering) assessed weekly were examined as causally preceding weekly measures of symptom change in the recent 16-session trial.¹⁴¹ Findings indicated that improvements in decentering temporally preceded changes in worry and trait anxiety, while improvements in reappraisal preceded reductions in worry, trait anxiety, and generalized anxiety symptoms and were associated with increases in decentering and commensurate reductions in worry. We also examined indirect effects of regulatory skill building on outcome in our prior RCT of ERT for ICs²⁸ and found indices of regulatory ability, including metacognitive skills, mediated distress, worry, and burden in caregivers who received ERT-C compared to those in the waitlist control condition.²⁸ In another study¹⁴² utilizing more objective assessment, we examined a commonly used explicit emotion regulation task and found increased activation in neural areas associated with regulatory ability and corresponding increases in metacognitive abilities and decreased MDD severity. Similarly, ERT-linked rsFC findings revealed pre-treatment patterns of neural activation that predicted clinical response to ERT with respect to gains in decentering and reductions in worry.¹⁴³ These ERT-linked changes in resting state connectivity were associated with decreases in GAD and MDD diagnostic severity (r 's = 0.4-0.6) and increases in decentering and reappraisal (r 's = 0.3 -0.4).¹⁴⁰ In all, ERT-linked gains in metacognition are associated with treatment response in patients with distress disorders.

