Most of the measures used for evaluation during treatment/intervention were also completed during Baseline (T1) and are described in Section 9.0. Before each treatment session, caregiver participants will complete a set of measures: HADS, ACS, EQ-D, ERQ-R, COPE Active Coping subscale. Additional measures during treatment/intervention are described below:

Working Alliance Inventory-Short Form (WAI-SF) assesses the perceived strength of the treatment alliance felt by patient [189,190]. After the fourth treatment (ERT-C or CBT-C) session, enrolled caregivers will complete the *Working Alliance Inventory-Short Form (WAI-SF)* [189] which assesses the perceived strength of the treatment alliance felt by patient (Appendix H).

COPE, Active Coping Subscale consists of five items describing different coping strategies used by people when responding to stress. Participants will indicate how frequently they use active coping strategies by rating statements on a scale from “1 = I usually don't do this at all” to “4 = I usually do this a lot” [188] (Appendix H).

Credibility and Expectancy Questionnaire is a 6-item measure of participants' reactions to treatment and includes ratings of acceptability and belief about effectiveness that will be completed only at T2 [172,173]. This measure has been modified for the cancer caregiver population, has been used extensively in prior research, and has demonstrated strong psychometric properties [173] (Appendix H).

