Primary Analyses: We will assess gains in emotion regulation as well as reductions in anxiety and depressive symptoms via growth curve modeling. First, for both emotion regulation skills and outcomes, a series of traditional growth curve models will assess the effect of ERT-C (versus CBT-

[figure not shown]

Figure 2. The parallel process latent growth curve model for mediation of ERT-C on outcomes via emotion regulation skills (measured weekly).

C) on each potential mediator from the ACS, EQ-D, ERQ-R, and COPE instruments which are assessed weekly during the intervention. Next, for each outcome, similar growth curve models will be used to assess the overall effect (direct and indirect effects) of ERT-C on outcomes both during the intervention and at major timepoints. We will employ parallel process latent growth curve modeling (PP-LGCM [200]) to assess the mediational process provided by weekly data. In PP-LGCM, changes in potential mediators and changes in outcomes are both modeled in a single measurement model. This combination of growth curve methodology with structural equation

modeling efficiently utilizes the longitudinal data of both the mediators and outcome variables and is depicted for the single mediation variable case in Figure 2. Here, η_1 and η_3 represent the intercepts for the growth processes for the mediation and outcome measures, respectively; η_2 and η_4 represent the slopes for the mediation and outcome measures, respectively. Means for mediators and outcomes may be impacted by intervention and correlated. Trajectory of a mediator may be impacted by treatment and baseline outcome. Trajectory of the outcome may be impacted by treatment and with both baseline and trajectory of the mediator. The mediation hypothesis is supported if the product of α and β is significant [201], that is, if ERT-C drives change in the mediator and change in the mediator drives change in the outcome. This analysis will be conducted using M-Plus software.

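### For HADS, the Aim 2 mediation rule reads a concurrent slope-on-slope association as skills driving symptoms, a direction the planned model cannot establish

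*Combined protocol and SAP*

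**What the plan says.** Section 14.0, Aim 2 Primary Analyses, uses a parallel process latent growth curve model "to assess the mediational process provided by weekly data". In it, "changes in potential mediators and changes in outcomes are both modeled in a single measurement model". The structural paths are given in words. For the skill: "Trajectory of a mediator may be impacted by treatment and baseline outcome". For the outcome: "Trajectory of the outcome may be impacted by treatment and with both baseline and trajectory of the mediator". Mediation counts as supported when the product of α and β is significant, and the plan explains what that means: "that is, if ERT-C drives change in the mediator and change in the mediator drives change in the outcome".

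Section 11.0 fixes the timing: "Before each treatment session, caregiver participants will complete a set of measures: HADS, ACS, EQ-D, ERQ-R, COPE Active Coping subscale". Section 4.1 adds that the pre-session assessment is done on the day of the session.

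Section 14.0 contains no lagged path, no model with the direction reversed, and no sensitivity analysis for confounding between mediator and outcome. Section 3.0 reports that in earlier work weekly metacognitive skills "assessed weekly were examined as causally preceding weekly measures of symptom change in the recent 16-session trial". That is background, and no such analysis is planned for this trial.

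**The concern.** The arm is randomized, so α (arm to skill slope) has a causal reading. The skill slope is not randomized, so β (skill slope to symptom slope) is an association within arm between two self-reported trajectories over the same weeks. That association arises if better regulation lowers distress. It also arises if feeling less distressed raises ACS, EQ-D or ERQ-R ratings, or if something else moves both. Adjusting the skill slope for baseline outcome deals with starting severity, not with concurrent symptom change.

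If ERT-C also moves skill ratings more than CBT-C does, for whatever reason, α and β are both non-zero and the product can be significant with no skill-to-symptom path at all. What is at stake is the conclusion about mechanism. A treatment that lowered distress first and improved self-rated skills as a consequence could be reported as working through emotion regulation.

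**Working it through.** **Inputs from Section 14.0.** 240 caregivers randomized 1:1 with 20% attrition: 240 × 0.80 = 192, or 96 per arm. The planned arm difference on symptoms is d = 0.41 (Aim 1 power). The mediation test is the Sobel test, z = αβ / √(α²·SE(β)² + β²·SE(α)²).

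**Assumptions.** Two-sided 5% level (Aim 2 states none). Coupling γ between the slopes of 0.3 to 0.9. Residual covariances, because the path diagram (Figure 2) is not available.

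**1. The plan's own figure.** Aim 2 claims at least 80% power with paths of 0.39 and 0.26. With these as coefficients on a unit-SD predictor at n = 192, simulated Sobel power is 0.92 to 0.93, so the statement holds as a lower bound. With the arm-to-skill path read literally as Cohen's d between two arms, power is 0.57 (d = 0.39) or 0.37 (d = 0.26). With both paths read as d it is 0.15. The present point does not depend on this.

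**2. Reverse causation, slopes known without error.** Let arm shift the symptom slope by d, let the symptom slope move the skill slope by γ, and set the skill-to-symptom path to zero. With both slopes scaled to unit SD within arm:

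- apparent α = γ × d
- SE(α) = 2/√192 = 0.144
- expected z for α = γ × 0.41/0.144 ≈ 2.84γ

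β is significant in about 99% of runs or more, so the rule mostly follows α.

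| γ | expected z for α | chance that α is significant | simulated Sobel rate |
|---|---|---|---|
| 0.3 | 0.85 | 14% | 8% |
| 0.5 | 1.42 | 30% | 28% |
| 0.7 | 1.99 | 51% | 50% |
| 0.9 | 2.56 | 72% | 72% |

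With d = 0 the Sobel rate is 3% to 5%.

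**3. Reverse causation, planned model fitted.** The parallel process model was fitted by maximum likelihood to 8 weekly scores per process, with 100 to 150 fits per setting.

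| d | γ | truth | rule positive |
|---|---|---|---|
| 0.41 | 0.5 | reverse | 14% |
| 0.41 | 0.7 | reverse | 31% |
| 0.41 | 0.9 | reverse | 58% |
| 0 | 0.7 | reverse | 4% |
| 0.41 | 0.7 | true mediation | 49% |

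Simulation error is about 3 to 5 percentage points. At γ = 0.7, 49% positive under true mediation against 31% under the reverse is weak discrimination.

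**4. Can fit settle the direction?** The slope arrow was swapped and the model refitted to the same data, 40 times under reverse causation. The median difference in log-likelihood was 0.0, with an interquartile range of 0 to 0. Fit carries no information on direction.

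**5. Shared cause.** If arm moves both slopes by 0.41 and they are merely correlated (0.3 to 0.7) with no path either way, the rule is positive in 72% to 81% (slopes known). If arm does not move the skill slope, it stays at or below about 5%.

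**The case against.** The method is established and cited, its direction is prespecified, and Section 3.0 reports earlier evidence that skill change came before symptom change. That justifies the choice of model. It does not let this trial's product test confirm the direction.

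Hypothesis 2a is a specificity check: attention and metacognitive skills should mediate while burden and coping should not, and COPE is modelled as a competing mediator. Mood relief that lifted every self-rating would tend to contradict 2a. This stands as a partial safeguard, but it does not test direction.

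Four stronger readings are tempting, and the documents do not support them.

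- **The rule declares mediation whenever the slopes are correlated.** It does not. A shared person-level cause leaves the randomized α at zero, and the false-positive rate then stays near nominal.
- **The flaw covers every Aim 2 outcome.** The same-weeks argument holds for HADS. PSWQ, the rumination scale, CQOLC and CRA are collected only at T1 to T4, so these rates do not carry over to them.
- **The trial's efficacy conclusion is affected.** Aim 2 plays no part in the superiority rules of Sections 13.1 and 14.0.
- **A significant lagged path should be required before mediation is supported.** Time-ordering is not a clean cure. Under a shared improvement rate with no causal path, a two-stage lagged path fired falsely in 28% to 60% of simulated trials. A cross-lagged model with person intercepts only did so in 34 of 34 fits and in 93% of 60 fits, at two noise levels. Under reverse causation the two-stage path still fired in 13% to 42%. Requiring both it and the product cut power from about 53–63% to 8–29%.

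**Conclusion.** The concern holds for HADS. The planned product test cannot show direction, and the plan's causal wording claims more than the model can deliver. At the plan's own n = 192 and d = 0.41, with coupling of 0.5 to 0.9 and no skill-to-symptom path, the fitted rule supports mediation in roughly 14% to 58% of trials against an assumed nominal 5%. The error needs a real arm difference and moderate to strong coupling. The coupling values and residual structure are assumptions with no source in the documents, so these rates show a plausible range and do not predict what this trial will find. The identical fit with the arrow reversed does not depend on a particular coupling value, although it was checked in one assumed specification.

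**What to change.** Keep the parallel process model as the primary Aim 2 analysis and amend Section 14.0 as follows.

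1. Replace the causal reading of a significant product with: the result is consistent with mediation (parallel change) and does not by itself establish direction.
2. Prespecify two labelled sensitivity analyses for HADS on the weekly data already scheduled:
   - (a) the same model with the slope path reversed, reported beside the forward model to show that both directions are compatible with the data;
   - (b) a time-ordered model that estimates both the skill-to-symptom and the symptom-to-skill lagged paths and allows for person-specific trends, not intercepts alone.
3. Use directional language only if the forward lagged path is supported and the reverse path does not explain the result. State in either case that residual mediator-outcome confounding remains.
4. Do not make the lagged test a mandatory gate for Aim 2.

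The change should be made before unblinded analysis. It needs no new visits, measures or participants. The costs are one or two more models, low power for the time-ordered test, and a more modest conclusion about mechanism.

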14.0 BIOSTATISTICS

This study is a psychotherapy RCT implemented at 2 clinical sites, with a 1:1 allocation of ERT-C to CBT-C. We propose to enroll 240 caregivers into either ERT-C or CBT-C. Caregiver participants will be assessed at pre-intervention (T1), post-intervention (T2), and at 3-months (T3) and 6-months (T4) follow-up for primary outcomes and mid-intervention at weekly therapeutic sessions for mechanistic measures and the HADS depression and anxiety outcomes. Up to 240 patients (for whom the caregiver is enrolled) will complete a short battery of assessments at T1 and T3. The four primary outcomes include caregiver depression, anxiety, worry, and rumination. Secondary outcomes include other caregiver and patient psychosocial and QOL measures. The primary analytic approach to testing the treatment efficacy in Aim 1 and change in biomarkers in Aim 3 will be Generalized Linear Mixed-Effects Model (GLIMMIX¹⁹¹), also known as Hierarchical Linear Model (HLM¹⁹²). For Aim 2, we will use an analytic strategy known as parallel process latent growth curve modeling (PP-LGCM), which is similar to a combination of growth curve models with the Baron and Kenney¹⁹³ approach, to test mediation of ERT-C on anxiety and depression via emotion regulation skills. PP-LGCM allows tests of both direct and indirect effects of treatment on outcomes through hypothesized pathways.

The statistics for the aims are described as follows:

AIM 1: Immediate and Longer-Term Efficacy of ERT-C vs. CBT-C in Improving Symptoms of Anxiety, Depression, Rumination and Worry.

Treatment-related improvements in anxiety, depression, worry and rumination symptoms (primary outcomes) and caregiver quality of life and burden (secondary outcomes) will be assessed by comparing measures at baseline, post-treatment, and at 3- and 6-months follow-up between ERT-C and CBT-C.

Hypothesis 1a: ERT-C will result in greater improvement in caregiver primary (i.e., anxiety and depression, worry, rumination) and secondary (i.e., QOL and burden) outcomes and these gains will be maintained at 6-months follow-up.

Hypothesis 1b: ERT-C will lead to greater improvements in cancer patient outcomes as compared to CBT at 3-months follow-up.

Exploratory Hypothesis 1c: Assess putative moderators of the efficacy of ERT-C versus CBT-C.

Primary Analyses:

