Power and Sample Size for Aim 2. Statistical power for mediation models was estimated from simulations by Fritz and MacKinnon, [202] which provide conservative estimates given the reduction in noise provided by our weekly assessments and growth curve modeling. Allowing for up to 20% attrition, the sample will provide at least 80% power to detect mediation using the Sobel test if one of the two paths (α or β) has a small-medium effect size (Cohen's $d=0.39$), and the other has at least a small effect ($d=0.26$).

Aim 3: Differential Effects of Treatment on Change in Biomarkers. We will describe and test differential changes in inflammation and salivary biomarkers overall and by treatment arm.

Hypothesis 3a: ERT-C will result in greater reductions in cortisol dysregulation and systemic inflammation as compared to CBT-C and gains will be maintained at 6-months follow-up.

Exploratory Hypothesis 3b: Reductions in cortisol dysregulation and systemic inflammation observed with ERT-C will be most prominent in caregivers with baseline elevations in distress.

Primary Analyses: The same HLM/GLIMMIX framework from Aim 1 will be used for Aim 3. Transformations may be needed for both biomarkers. The analysis will be similarly conducted to assess both differential pre-post change (T1 to T2) and also maintenance at 6-months follow-up (T2 to T4), using appropriate contrasts on the time variable. This same framework will allow for testing the exploratory moderation hypothesis. Specifically, for Hypothesis 3b, outcomes will be regressed on the ERT-C indicator, an indicator of elevated baseline distress, and the interaction of the two. A significant finding on the interaction term will be evidence to a moderation effect and will be followed with stratified analyses of the biomarker outcomes by baseline distress category and treatment arm.

Power and Sample Size for Aim 3. Based on previous participation rates with biological samples at our institutions, we anticipate at least 75% of the 240 enrolled caregivers to provide samples. With a conservative 20% attrition assumption, an analytic sample of $n=144$ would provide 80% power to detect a small-medium effect size of $d=0.36$ for the t-test for Hypothesis 3a.

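### The Aim 2 claim of at least 80% Sobel power does not follow from the stated Cohen's d values for a 1:1 arm comparison; it fits only if those values are path coefficients per SD of a continuous predictor

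*Combined protocol and SAP*

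**What the plan says.** Section 14.0 sets the design: "We propose to enroll 240 caregivers into either ERT-C or CBT-C", "with a 1:1 allocation of ERT-C to CBT-C".

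Under Aim 2, Primary Analyses, the model is a parallel-process latent growth curve. Alpha is the path from randomized arm to change in the mediator, and beta is the path from change in the mediator to change in the outcome. The criterion is: "The mediation hypothesis is supported if the product of α and β is significant".

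Under Power and Sample Size for Aim 2, the plan relies on published simulations of mediation power. "Allowing for up to 20% attrition", it states that "the sample will provide at least 80% power to detect mediation using the Sobel test if one of the two paths" has Cohen's d=0.39 and the other has at least d=0.26. Either path may carry the larger value. The same paragraph calls the estimate conservative because weekly assessments and growth modelling reduce noise. It gives no alpha level or sidedness for Aim 2, no size for that noise reduction, and no conversion between a two-group d and a regression coefficient.

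**The concern.** Cohen's d for a two-arm contrast fixes the power of the arm-to-mediator path once the number per arm is known. A test that needs both paths cannot do better than the weaker one. A quick check at 96 per arm puts the arm path below 80% for both stated values, so the product test should fall short as well.

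Aim 2 is the trial's mechanism claim, and Hypothesis 2a is selective: only certain regulatory skills should mediate. A selective claim depends partly on reading non-significant indirect effects as absence of mediation. If power is well below the stated figure, such nulls say little.

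**Working it through.** **Inputs**

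- Enrolled 240, allocated 1:1 (section 14.0). With 20% attrition: 240 × 0.8 = 192, or 96 per arm.
- Path effects 0.39 and 0.26, labelled Cohen's d, in either order (Power and Sample Size for Aim 2).
- Alpha: not stated for Aim 2. Two-sided 0.05 is assumed and varied below.
- Model: M = a·X + e₁, Y = b·M + e₂, with unit-variance errors, no direct effect and one measurement of each variable.

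**Step 1. Reproduce the plan's figure.** Take X as continuous with SD 1, and 0.39 and 0.26 as coefficients. With z = coefficient × √192, z_a = 0.39 × 13.86 = 5.40 and z_b = 0.26 × 13.86 = 3.60. The Sobel statistic is

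z_S = z_a z_b / √(z_a² + z_b²) = 5.40 × 3.60 / 6.49 ≈ 3.00.

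Simulated Sobel power is about 92% in either order, and 80% is reached at roughly n=145. On this reading the claim is met.

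**Step 2. Arm path with d as stated.** Power ≈ Φ(d√(96/2) − 1.96).

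- d=0.39: 0.39 × 6.928 = 2.702; Φ(0.742) = 77.1% (noncentral t 76.7%).
- d=0.26: 0.26 × 6.928 = 1.801; Φ(−0.159) = 43.7% (noncentral t 43.3%; simulations 43-45%).

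**Step 3. Ceiling.** |z_S| is always smaller than both |z_a| and |z_b|. In this model Sobel power therefore cannot exceed the Step 2 values, apart from a trivial difference between z and t critical values. With a very large b (2.0), simulated Sobel power is 77.5% and 44.0%.

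**Step 4. Sobel power, n=192, 1:1 arm** (20,000 simulated trials per row; the expected z_S is a guide only)

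| Arm path (d) | Beta | Expected z_S | Sobel power | Both paths significant |
|---|---|---|---|---|
| 0.39 | 0.26, standardized slope | 2.16 | about 55% | about 72% |
| 0.26 | 0.39, standardized slope | 1.71 | 37-38% | about 44% |
| 0.39 | 0.13 (d=0.26 ÷ 2) | 1.50 | about 15% | about 33% |
| 0.26 | 0.195 (d=0.39 ÷ 2) | 1.50 | about 15% | about 33% |

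The last two rows put both paths on the d scale: r = d/√(d²+4), which gives a slope of r/√(1−r²) = d/2.

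**Step 5. Convert the values that do give the claim.** A 1:1 arm indicator has SD 0.5. A coefficient of 0.39 per SD is a group difference of 0.39/0.5 = 0.78, and 0.26 per SD is 0.26/0.5 = 0.52. These are twice the printed d values.

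**Step 6. Arm effect giving 80% Sobel power at n=192.** About d=0.43 with beta=0.39, or about d=0.53 with beta=0.26.

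**Step 7. Variants, beta as a standardized slope** (arm d=0.39 first, then 0.26)

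- One-sided 0.05, n=192: arm path 85% and 56%; Sobel 74% and 53%.
- Two-sided 0.0125, n=192: arm path alone 58% and 24%.
- No attrition, n=240, two-sided 0.05: Sobel 72% and 47%.
- No attrition, one-sided 0.05: Sobel 86% and 62%.

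No variant that keeps the 20% attrition reaches 80%. The single case above 80% drops the attrition, is one-sided, and covers only one of the two orders that the plan claims.

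**The case against.** The strongest reply is that the planned analysis is not the model checked here. Mediators are measured before each of eight sessions as well as at T1 and T2, and the plan says the published simulations are conservative for that reason. The gain could be real. As an illustration, read d as the end-of-treatment difference in single-assessment SD units, borrow the Aim 1 ICC of 0.2, and allow a random intercept only, with 10 equally spaced assessments. With time scaled 0 to 1, Σ(t − t̄)² = 1.0185, so the standard error of the arm difference in slope is √[(0.8/1.0185) × 2/96] = 0.128. Arm-path power is then Φ(0.39/0.128 − 1.96) = 86% and Φ(0.26/0.128 − 1.96) = 53%.

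This part stands: a reader might infer that 80% power is unattainable in this trial, and the documents do not support that. The 43-77% range is a ceiling for the single-measurement model, not for the growth model. The illustration does not establish the claim either. It omits random slopes, which would shrink the gain, it borrows an ICC set for another purpose, and it gives arm-path power rather than Sobel power. The plan also does not offer weekly data as the source of the 80%. It treats the published simulations as sufficient already and the weekly data as a margin. In d units for a binary arm, that base calculation does not give 80%.

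A second reply is that 0.39 and 0.26 are really path coefficients. That is the likely explanation, and on that reading the calculation is sound. The text would still misstate the detectable arm effect by a factor of about two. Elsewhere in section 14.0, d denotes a between-arm difference.

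It is also true that Aim 2 is not the primary efficacy aim and that neither the sample size nor the superiority rule depends on this sentence.

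**Conclusion.** The statement of at least 80% power is not supported in the units in which it is written. Under a single-mediator model with a 1:1 arm, n=192 and an assumed two-sided 0.05, Sobel power is about 55% or 37-38% with beta as a standardized slope, and about 15% with both paths in d. The figure is reproduced only with coefficients per SD of a continuous predictor, equivalent to arm effects of about d=0.78 and 0.52.

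Two further inferences should be avoided. One is that power is overstated by a fixed 25 to 43 points (80 − 55 and 80 − 37): those gaps pair a d-scale alpha with a standardized-slope beta at an assumed significance level. The other is that 0.52 and 0.78 are the arm effects needed for 80% power. They are unit conversions, and paired with the other stated coefficient each gives about 92%. The 80% points are about 0.43 and 0.53, as in Step 6.

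Confidence is high that the units and the stated power do not agree. It is lower on the true power of the planned growth model, which the documents do not allow one to compute.

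**What to change.** In Power and Sample Size for Aim 2:

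1. State whether 0.39 and 0.26 are Cohen's d or standardized coefficients, and for which path, and give the alpha level and sidedness.
2. Restate power for a 1:1 arm indicator. Under the single-mediator model at n=192 and two-sided 0.05, 80% Sobel power needs an arm effect of about d=0.43 with beta=0.39, or about d=0.53 with beta=0.26. Alternatively, simulate the planned parallel-process growth model, with its assumed ICC, slope variance and attrition, and report that figure in place of the general remark about noise reduction.
3. Optionally, judge the product of alpha and beta by a bootstrap or Monte Carlo confidence interval instead of the Sobel z. Requiring both paths to be significant, used here as a proxy for such intervals, gives about 72% against 55% and 44% against 38% in the same model. The gain from the interval itself was not simulated.

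The cost is a corrected paragraph and, if chosen, one simulation exercise. The interval option means slightly longer run time. Sample size, data collection and participant burden do not change.
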